1.0 SUMMARY of INVESTIGATION

Study Title:	Prospective, Parallel, Multicenter Randomized Controlled Study Investigating the Effects of UVC Beam and Laser Beam Therapy According to Standard Therapy in Patients with Covid-19 Diagnosis
Study Code:	MD2020/001
Device :	Turkishbeam Model Number: 1007-001
	*: The device was produced by RD GLOBAL ARASTIRMA GELISTIRME SAĞLIK ILAÇ INSAAT YATIRIMLARI A.S.
Device Classification:	Class III
Purpose of the Study:	Clinical research study that evaluates the effect of Turkish Beam- Selective UV developed by RD GLOBAL ARASTIRMA GELISTIRME SAĞLIK ILAÇ INSAAT YATIRIMLARI A.S. use into Intravascular, Intrapulmonary, Intratracial, Intrarespiratory area. Bacteria, Fungal and Virus-based pathogens systematically to collect and evaluate specific clinical performance and safety data. In our Clinical Research, we aimed to investigate the effectiveness of the treatment group and control group mortality rates, intensive care hospitalization times, monitoring the virus load by PCR, and the treatment effectiveness of UVC

Scope of the Study:	This Clinical Research covers determining the treatment effectiveness and reliability of UVC application to patient groups, the details of which are determined in the protocol.
Application:	Intravascular, Intrapulmonary, Intratracial, Intrarespiratory UVC and Laser Therapy System
Overall Study Design:	Prospective, Parellel, Multicenter, Randomized Controlled
Number of volunteers:	50 patient- 2 groups with 25 (two hundred) patients in each group
Treatment Groups:	Test: Antiviral + Antimalarial + Antibiotic Treatment + UVC Therapy Control: Antiviral + Antimalarial + Antibiotic Treatment
Groups of Volunteer:	Those who are between the ages of 40-75 and who have applied to the clinic with symptoms such as fever, weakness, cough, and shortness of breath, or who have signs of COVID-19 (SARS- CoV-2) test positive or atypical pneumonia findings in CT findings and accepted as COVID 19 infection, and patients undergoing intubation treatment in intensive care unit
Sensitive population / Vulnerable subjects:	The study will not include under-40, pregnant women and those with suspected pregnancy, previously diagnosed with mental disorders, puerperant women and lactating women

Duration of the clinical trial: 3 months (04.2020- 07.2020)

Researched Medical Condition:

and Disease

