5.2 Inclusion Criteria

- Respiratory rate ≥ 30

- Dyspnea and breathing difficulties findings

- Cases with oxygen saturation below 90% despite nasal oxygen support of 5 liters / minute and above

- Cases with partial oxygen pressure below 70 mmHg despite nasal oxygen support of 5 liters / minute and above

- PaO2 / FiO2 <300

Lactate> 4 *mmol* / *L*

Bilateral infiltrations or multi-lobar involvement on chest x-ray or tomography

- Hypotension (systolic blood pressure <90 mmHg,> 40 mmHg drop from usual SKB, mean arterial pressure <65 mmHg)

- Skin perfusion disorder

Organ dysfunction such as kidney function test, liver function test disorder, thrombocytopenia, confusion

Presence of immunosuppressive disease-

Presence of uncontrolled comorbidity with more than one feature

- Troponin height, arrhythmia
- COVID 19 Test positivity

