5.6 Secondary Endpoints

- Hypersensitivity
- Temporary shortness of breath
- Rarely, redness of the skin is due to heat
- Edema
- Bleeding
- Embolization
- Hematoma
- Hyperpigmentation
- Ache
- paresthesia
- Superficial thrombophlebitis
- May cause urticaria or ulcers.
- Vascular rupture and perforation
- Visible scratch
- Iatrogenic injury may damage the surrounding tissues.
- Hemothorax or pneumothorax.
- Neighboring Nerve Damage Iatrogenically
- phlebitis
- Skin Burn or discoloration

If two or more adverse effects from the above adverse effects are seen, the study is terminated.

6. Statistical Evaluation:

- According to the course of the clinical trial, if we reach the research arm (100 patients), control group (100 patients), the efficacy and safety of the treatment will be examined and an interim report will be prepared. According to the results of the interim report, the clinical trial will be terminated or the clinical trial will be continued until the number of volunteers (400 in total) mentioned above is completed.
- In this interim analysis, the patients completing the study will be evaluated considering the primary and secondary endpoints stated in the protocol and the criteria are as follows:

1-Duration in intensive care

2-Survival rate

Contribution of UVC and laser beam application to the treatment of 3-COVID 19 infection and / or superinfections accompanying COVID 19 infection

The tests to be applied are as follows:

1-Difference test between two averages for intensive care stay

(Mann-Whitney U test or t test) will be used.

2-Survival analysis tests will be used for survival rate.

Accompanying 3-COVID 19 infection treatment and / or COVID 19 infection

To investigate the contribution of UVC and laser beam application to the treatment of superinfections

Chi-square test will be applied.

Descriptive statistics will also be given for demographic data.

REFERENCE STUDIES ABOUT THE APPLICATION OF UVC BEAM "in vitro, in vivo and ex vivo"

1. The Effect of UV-C Ray Reducing Pathogen Rate on Blood Platelets Apps;

Auto-immune diseases HIV 1 -2
T-lymphotropic virus types 1 and 2
Hepatitis B (HBV)
Hepatitis C (HCV)
Hepatitis A and E
Blood pathogens (Treponema pallidum)
Parvovirus B19

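### The plan names no baseline adjustment although age and Day 0 severity data are scheduled; the cost is precision and exposure to chance imbalance, chiefly at 25 per arm

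*Combined protocol and SAP*

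**What the plan says.** Section 6 (Statistical Evaluation) is the whole analysis plan. Its list of tests is introduced for the interim analysis, and no other list is given for the final one.

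- **ICU stay:** a two-sample comparison of averages, "Mann-Whitney U test or t test) will be used".
- **Survival:** "2-Survival analysis tests will be used for survival rate". No method, model or covariate is named.
- **Infection or superinfection outcome:** a chi-square test.
- **Baseline data:** "Descriptive statistics will also be given for demographic data".

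The design line in Section 1.0 reads "Prospective, Parellel, Multicenter, Randomized Controlled". No stratified or minimised randomisation is described.

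The patients vary. Ages run from 40 to 75, and the entry list in Section 5.2 ranges over oxygenation, lactate, hypotension, organ dysfunction and immunosuppression. The visit schedule in Section 5.4 has demographics at screening. It has vital signs, biochemistry with blood count, and imaging at both Day 0 columns.

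The sample size is stated inconsistently. Section 1.0 gives "50 patient- 2 groups with 25 (two hundred) patients in each group". Section 6 places the interim report "if we reach the research arm (100 patients), control group (100 patients", and otherwise "the clinical trial will be continued until the number of volunteers (400 in total) mentioned above is completed".

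**The concern.** Neither the randomisation, as described, nor the analysis uses baseline prognosis. The protocol itself treats prognosis as varied. Its background in Section 4.6 links severe and lethal disease to older age and weakened immunity, and uses several severity measures as indications for intensive care. Age and severity are thus natural candidates as predictors of death and ICU stay.

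Two things are at stake. First, in a small trial one arm may by chance be older or sicker, and an unadjusted estimate then carries that difference with no planned analysis to separate it from the treatment effect. Second, outcome variation that age and severity could explain stays in the error term. If adjustment is added only after the data are seen, the choice of covariates becomes a matter of discretion.

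**Working it through.** **Inputs from the document:** two equal arms; 25 per arm (Section 1.0), 100 per arm at the interim and 400 in total (Section 6), the last taken here as 200 per arm. The document states no alpha, power, effect size, SD, event rate or covariate strength, so there is no planned power figure to reproduce.

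**Assumptions:** two-sided alpha 0.05; simple randomisation; effect 0.7 SD; share of outcome variance explained by two covariates (R²) from 0 to 0.4.

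**1. Chance imbalance.** The standardised difference between arms in one covariate has standard deviation √(2/n), with n per arm. The chance of exceeding c is 2[1 − Φ(c/√(2/n))].

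| n per arm | √(2/n) | over 0.25 SD | over 0.5 SD |
|---|---|---|---|
| 25 | 0.283 | 37.7% | 7.7% |
| 100 | 0.141 | 7.7% | 0.04% |
| 200 | 0.100 | 1.2% | about 0 |

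A 0.5 SD imbalance in a covariate with explained share R² shifts the unadjusted estimate by 0.5 × √R². That is 0.16, 0.22 and 0.27 outcome SD at R² of 0.1, 0.2 and 0.3.

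**2. Power for a continuous outcome, 25 per arm.**

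- Unadjusted: noncentrality 0.7/√(2/25) = 2.475 on 48 degrees of freedom, power 67.9%.
- Adjusted for two covariates: 46 degrees of freedom. The residual variance is multiplied by (1 − R²), and the variance of the estimate by a small-sample penalty of 47/45 = 1.044. Noncentrality is 2.475/√[1.044(1 − R²)].

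| R² | noncentrality | power |
|---|---|---|
| 0 | 2.422 | 65.9% |
| 0.05 | 2.485 | 68.2% |
| 0.1 | 2.553 | 70.5% |
| 0.2 | 2.707 | 75.5% |
| 0.4 | 3.126 | 86.4% |

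Expressed as patients, 50/[1.044(1 − R²)] gives about 53 at R² 0.1, 60 at 0.2 and 80 at 0.4. At R² 0 it gives about 48.

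At 200 per arm, unadjusted power for 0.7 SD is already about 100%. A gain remains only for smaller effects: for 0.3 SD, power goes from 85% to 92% at R² 0.2.

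**3. Survival.** The variance formula in step 2 belongs to a linear model, so a Cox model was simulated separately at 25 per arm (2,000 runs). The assumptions were 50% control mortality by Day 15 and log hazard ratios of 0.4 per SD for age and 0.7 per SD for severity.

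| True hazard ratio | mean deaths | unadjusted rejects | adjusted rejects |
|---|---|---|---|
| 1.0 | 25.2 | 5.0% | 5.6% |
| 0.5 | 20.4 | 23.6% | 30.4% |
| 0.4 | 19.1 | 36.3% | 45.0% |

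**4. Availability of the covariates.** Age is certain. Vital signs and biochemistry are scheduled for all on Day 0. Imaging is scheduled too, but the text below the schedule allows for patients who cannot have it. Oxygenation, "PaO2 / FiO2 <300", is one item in an entry list with no and/or rule. It has no row in the visit schedule, and no blood gas appears in the list of blood tests.

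**The case against.** The strongest defence is that nothing here is invalid. Randomisation protects the unadjusted tests, chance imbalance is already allowed for in their error rates, and the gain rests on an R² that the document does not give. If the covariates explain about 5% or less, adjustment gains nothing or loses slightly. All of this stands, and it makes the point one of efficiency rather than validity.

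Five stronger readings are tempting, and the document does not support them:

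- **That every planned comparison is unadjusted.** This is true of the tests named for ICU stay and infection outcome. For survival the method is missing; a Cox model with covariates is neither stated nor excluded.
- **That the unadjusted tests inflate type I error.** They do not. The simulation gave 5.0% unadjusted.
- **That 25 per arm is settled.** The same line says two hundred, and Section 6 implies 200 per arm. At that size the imbalance argument nearly vanishes.
- **That PaO2/FiO2 is on record at Day 0 for everyone.** A patient might enter on another criterion, and no scheduled assessment captures the ratio.
- **That the continuous-outcome gain applies to survival.** It does not transfer, and at 25 per arm the simulated survival comparison stays underpowered with or without adjustment.

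What survives is that prognostic data are scheduled, the plan makes no use of them in any stated comparison, and naming two covariates in advance costs very little.

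**Conclusion.** The point holds as a recommendation to improve a valid but needlessly imprecise plan. Its weight depends on which sample size is meant. At 25 per arm, a difference over 0.25 SD in a given covariate has a 38% chance, and adjustment would move power for an assumed 0.7 SD difference from 68% to about 71-86% over an assumed R² of 0.1 to 0.4. The downside is about 2 points if the covariates are not prognostic. At 200 per arm the imbalance chance is 1.2% and the power gain is confined to smaller effects. The effect size, R², mortality and covariate hazard ratios are all assumptions. The imbalance figures need only simple randomisation and the stated arm sizes, with a normal approximation.

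**What to change.** 1. **Reconcile the sample size** between Sections 1.0 and 6, since it decides how much the rest matters.
2. **Name two covariates before any comparative data are seen:** age and one Day 0 severity measure recorded for all patients. Use PaO2/FiO2 only if its Day 0 recording for everyone is confirmed; otherwise use a scheduled Day 0 vital sign or laboratory value. Give the measure, its scale and the handling of a missing value.
3. **Name the models:** Cox regression for survival, a linear model on log or rank-transformed ICU stay (state which), and logistic regression for the infection outcome, each with arm and the same two covariates.
4. **Keep the unadjusted tests as supportive analyses.** State that the adjusted hazard and odds ratios are conditional on the covariates and need not equal the unadjusted ones.
5. **Stop at two covariates if the trial has 50 patients.** Under the assumed 50% control mortality only about 20 to 25 deaths are expected.

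The cost is SAP wording, two degrees of freedom and, if PaO2/FiO2 is chosen, possibly one case-report-form line. With a scheduled measure no new data are needed.
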